#### **4.2 Patient Consent**

The NYU study staff will be recruiting and consenting the participant by reading the approved telephone verbal informed consent script to the participant. The study staff will first complete a brief phone screener to screen whether or not the participant is eligible. Once eligibility is confirmed, the study staff will discuss with the patient what active participation in this study means (review verbal consent, interviews, potential benefits, and risks of participation), the purpose and limitations of the study, and requirements of the study. If the patients verbally agree to participate, the patient's primary care physician will also be notified that the patient is being enrolled in this study. The verbal consent will be audiotaped with the patient's permission. The verbal consent is an accommodation due to the rising COVID-19 infection rate in New York, and that the target population for this study is low-income aging immigrants with limited education and low digital literacy. All interventions will be conducted via phone or text message. A waiver of documentation of consent has been requested.

The study team has requested a waiver of signed HIPAA authorization and all HIPAA information will be presented verbally.

An IRB-approved verbal consent script will be used and will include the HIPAA and audio recording information, the subject will verbalize comprehension of the consent form and study enrollment. The consent process will be recorded via audio the consent and the date of consent will be documented on the Enrolled Participants Log. The Enrolled Participants Log is the only record linking a participant's name and Subject ID, this information will be kept on a secure electronic drive to ensure the confidentiality of health information and identifying information from participants. Only the principal investigator and all members of the research team will have access to this information and the audio recordings of their verbal consent.

We will have the verbal consent script available in both English and Chinese. The participant can choose their own preferred language and our bilingual study staff will explain the study to the participant. The participant will be encouraged to ask any questions they may have before providing the verbal consent.

After verbal consent is obtained, we will ask both patients and family/friend participants if we can send them via text message a copy of the key information sheet for their records before we collect any data from them.

The Informed Consent is a continuous and dynamic process, all participants will be reminded at every phone call about the A/V recordings, study assessments and that they are free to withdraw at any time.

#### **4.3 Study Procedures**

The proposed study is a pilot randomized controlled trial (RCT) of 6 months duration. Participants will be randomized to one of 2 arms (n=15 pairs each): 1) wait-list control; or 2) SMS intervention. The study will include 3 telephone-based measurement visits, baseline, 3, and 6 months. For patient participant, during each telephone visit, we will ask them some survey questionnaires. Once we receive their consent, we will also contact their doctors' office to obtain HbA1c results. For family/friend participant, each telephone visit will only have some survey

questionnaires. At the end of the 3-month intervention, we will randomly select 10-20 patient and family member participants to join a focus group/interview study to understand their experience with our intervention. Both patient and their family member will be paid \$30 for each measurement visit.

Upon receiving the referral list (interested patient's name and phone number) from the providers, the bilingual study staff will call the patient and provide more details about the study. If patients expressed interest in participation, the study staff will administer several screening questions over the phone. After eligibility is determined, we will ask patients to talk to their family members or friends about this study and confirmed their family/friends interests in participation. Once we received call back from patients confirming their own as well as their family members/friends' interests', we will schedule an appointment to obtain verbal consent from both and collect baseline data. The patient and family/friend pair will be randomized via a computer-generated randomization scheme with equal allocation to one of the 2 groups: 1) wait-list control; or 2) SMS.

**Independent variable: randomization arm**

**Wait-list control group: For patient participants**, they will continue to receive the standard of usual care for their T2D at the NYC health care facilities during the course of our study. For family/friend participants, they will continue to receive their routine care with their own doctors during the study. At the end of the study, the wait-list control group (both patient and family/friend participants) will be provided the opportunity to receive the counseling videos delivered to them via SMS links.

**SMS or WeChat intervention:** We will send 2-3 diabetes videos every week for 12 weeks (each video about 5-10 minutes in duration) to both patients and their family members via WeChat or regular text messages (SMS). We will contact participants mainly through phone calls from NYU Langone Study Phone. WeChat will be only used to send the health education videos. No other communication will occur via WeChat. Our study team will remind participants at the beginning of the study and during the bi-weekly phone calls about not sending any Protected Health Information via WeChat. In addition, our education videos do not contain any Protected Health Information and it will teach participants about diet, exercise, and stress management in general. We will ask participants' permission to use WeChat platform and advise that sending messages over an unsecured application like WeChat is an unsecure and unencrypted form of communication and there is a potential risk of disclosing information to an individual who is not authorized to receive it (unauthorized disclosure).

We will also let participants know that they can still participate in the study if they decline to receive the health education videos on WeChat. As an alternative, we will send the education videos as regular text messages to their phones. They can decline at any time during the study to receive the videos on WeChat and then we will switch to regular text messages.

Patients and their family members will receive the same intervention videos, including basic information about T2D, importance of diabetes self-management at home, behavioral techniques, and family-oriented sessions. For participants who miss 3 consecutive videos, the study team will follow-up with a phone call to identify barriers to watching the video and remind them to review the video. We will also help patient participants to set goals for their diabetes management and then have biweekly phone call follow-ups to check in their progress toward the goal and problem solve any raised questions/concerns.

**Procedures:** The study will include 3 measurement telephone visits, baseline, 3, and 6 months. Each session will include audio/Video recordings if verbal consent from the study participants was obtained. Both patient and family/friend participants will be paid \$30 for each telephone visit. All data will be collected during the telephone visit. For patient participants, each visit will involve completion of questionnaires. After obtaining patients' consent, we will contact their doctors' office to obtain HbA1c results. For family/friend participants, each visit will only involve completion of questionnaires. For family/friend participants in the intervention group, we will send them diabetes education videos to help them obtain more information about diabetes, which allows them to better support patients in their disease management. For participants randomized to the SMS intervention group, we will reimburse \$5 each week to each participant for cell phone data usage if they finish viewing both of the sent videos for that week. Given that we will send videos over a total of 12 weeks, participants may expect to receive a range of \$0-\$60 ( $=\$5*12$ ) depending on the number of weeks they have completed the videos. We will also provide \$60 to control participants if they finish all study related procedures at 3 months assessment.

At the end of 3-month intervention, we will host 2 focus group discussions to understand their experience with our study. One focus group will invite highly engaged participants, defined as who have watched at least 80% of the diabetes videos. The other focus group is with poorly engaged group, defined as participants who have watched less than 80% of the videos. Each participant will receive \$30 for their participation in the focus group. If it is challenging to identify a time that works for everyone, we will offer individual interview to those who have limited availability. After finishing the interview, they will also receive \$30 as incentives.

[figure not shown]

Figure 1. Conceptual Model

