#### 3.3. Characteristics of the Research Population

We will recruit **60 participants for this project**, including 30 T2D Chinese patients and 30 corresponding family members. Family member is broadly defined as any support person who the patient considers plays a vital role in their diabetes self-management and would be interested in receiving such interventions. This can be spouse, adult children, siblings, or friends.

**Inclusion criteria for patient participants:** To be eligible for the study, patient participants must: 1) self-identify as Chinese immigrant or Chinese American; 2) be between the ages of 18 and 70; 3) be able to speak and understand Mandarin; 4) self-report a diagnosis of T2D; 5) baseline HbA1c  $\geq 7\%$ ; 6) be currently using WeChat; 7) be willing to receive WeChat or text messages regarding T2D management; 8) express strong interest and confidence in finishing watching 2 diabetes videos each week for a total of 12 weeks; 9) be motivated to make lifestyle changes to control their diabetes; and 10) have a family member or friend be willing to participate in the study to learn about T2D to better support them.

**Inclusion criteria for family/friend participants:** Family/friend participants must 1) self-identify as Chinese immigrant or Chinese American; 2) be between 18-70 years old; 3) be able to speak and understand Mandarin; 4) be currently using WeChat or text messages; 5) be willing to receive WeChat or text messages regarding T2D management and learn how to better support the patient with T2D; 6) express strong interest and confidence in finishing watching 2 diabetes videos each week for a total of 12 weeks; and 7) be motivated to support their family/friend to make lifestyle changes to control their diabetes.

**Exclusion criteria for both patient and family/friend participants:** Individuals will be excluded from participation if they meet any of the following: (1) unable or unwilling to provide verbal consent; (2) unable to participate meaningfully in the intervention (e.g., uncorrected sight and hearing impairment); (3) unwilling to accept randomization assignment; (4) pregnant, plans to become pregnant in the next 6 months, or who become pregnant during the study, (5) breastfeeding, or (6) live in a facility or other health care setting where they have no control over diabetes self-management.

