### Primary & Exploratory Outcomes

**Primary outcome: Feasibility:** Feasibility will be examined by calculating the percent of videos sent that are watched. We will also assess the feasibility by determining whether we are able to meet our recruitment goal of 30 Chinese American families and reach 80% retention rate.

**Acceptability:** Acceptability will be assessed using a satisfaction questionnaire adapted from a prior SMS intervention study.

**Secondary outcomes:** Consistent with our conceptual model (Fig. 1), we will also measure HbA1c, self-efficacy, and diabetes self-management behaviors at each time points (baseline, 3-, and 6-months). All of these scales have been used and validated in the Chinese population.

1. **HbA1c:** As part of the usual care, patients with T2D receive a HbA1c blood test at their doctors' office every 3-6 months. To minimize participants' burden, we will not conduct additional blood tests for this study. Instead, we will abstract the HbA1c testing results from the medical record at the participant's health care facility. Once we obtain the consent from participants, we will contact their doctors' offices for HbA1c results.

2. **Self-efficacy:** We will use the well-validated Stanford Diabetes Self-Efficacy Scale to measure participants' confidence to manage T2D. This instrument contains 8 items and asks participants to rate their confidence level in performing specific self-management behaviors, using 10-point Likert scale ranging from 1 (not at all confident) to 10 (totally confident).
3. **Diabetes Self-Management Behaviors:** We will administer the adapted Summary of Diabetes Self-Care Activities (SDSCA) measure to assess participants' adherence to diabetes self-management behaviors. This scale consists of 13 items and asks participants to describe their diabetes self-care activities over the past 7 days.
4. **Dietary Intake:** Informed by a previous study in Chinese Americans, we will use the adapted Mediterranean Dietary Screener to estimate dietary intake behaviors in our participants at baseline, 3- and 6-months.

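### Does sending two or three videos a week leave the weekly payment rule and the viewing measures undefined?

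*Combined protocol and SAP*

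**What the plan says.** The weekly number of videos appears in three places in the combined protocol and SAP.

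- **Section 4.3, SMS or WeChat intervention:** "We will send 2-3 diabetes videos every week for 12 weeks". Patients and family members receive the same videos.
- **Section 3.3, both inclusion lists:** participants must "express strong interest and confidence in finishing watching 2 diabetes videos each week for a total of 12 weeks".
- **Section 4.3, Procedures:** each participant in the SMS arm receives $5 for a week "if they finish viewing both of the sent videos for that week". The total is given as $0 to $60, "depending on the number of weeks they have completed the videos".

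Two measures depend on how many videos are watched.

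- **Primary feasibility outcome** (section 4.3, Primary & Exploratory Outcomes, repeated in section 7.1): "Feasibility will be examined by calculating the percent of videos sent that are watched". No cut-off is attached to this percentage.
- **Focus groups** (section 4.3): the highly engaged group is "defined as who have watched at least 80% of the diabetes videos", and the other group is everyone below that level.

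**The concern.** Taken literally, *both* describes two videos, and the intervention description allows three. In a three-video week, a participant who watches two is paid if any two suffice and is not paid if all three are required. Nothing in the documents says which weeks carry three videos or whether a third is optional.

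The entry criterion names two a week, and on one reading the payment also stops at two, while the feasibility percentage counts a third. A participant who does what the entry criterion names could then score well below 100% on a primary outcome and be invited to the poorly engaged focus group. At stake would be uniform payment across the SMS arm (15 pairs, so 30 people) and the interpretation of the feasibility figure that is meant to inform a larger trial.

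**Working it through.** **Inputs.** Two or three videos a week for 12 weeks (section 4.3); two a week at entry (section 3.3); $5 a week (section 4.3); an 80% engagement cut-off (section 4.3). The number of three-video weeks, *k*, is not given, so the full range of 0 to 12 is taken as an assumption.

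**The plan's own figure.** $5 × 12 = $60. This matches the stated maximum and does not depend on *k*, because payment is by the week.

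**Videos sent.** 2 × 12 + *k* = 24 + *k*, so from 24 to 36.

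**A participant who watches exactly two every week.** The viewing percentage is 24/(24 + *k*). Payment is $60 if any two suffice, and $5 × (12 − *k*) if all videos sent are required.

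| *k* | Sent | Viewing percentage | Paid if any two suffice | Paid if all sent are required | Difference |
|---|---|---|---|---|---|
| 0 | 24 | 100% | $60 | $60 | $0 |
| 6 | 30 | 80.0% | $60 | $30 | $30 |
| 7 | 31 | 77.4% | $60 | $25 | $35 |
| 12 | 36 | 66.7% | $60 | $0 | $60 |

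The difference is $5 × *k*. The percentage falls below 80% only when 24/(24 + *k*) < 0.80, that is *k* > 6, so from seven three-video weeks upward.

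**Which reading the text supports.** The payment condition is attached to the videos sent that week, and the next sentence counts weeks in which the videos were completed. Two out of three is neither all the videos sent nor a completed week. Reading the two sentences together gives all videos sent, with *both* left over from a two-video week.

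**What the weekly number reaches.**

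- *Feasibility percentage:* numerator and denominator are both counts of sent videos, so it is defined for every *k*. Someone who watches two of three should score below 100%.
- *Focus-group cut-off:* the text gives no other set of videos for the 80% to refer to, so videos sent is the only available denominator.
- *Entry criterion:* it screens for interest and confidence and does not set a delivery schedule. A range of two to three includes two.
- *Sample size, alpha and the HbA1c mixed model:* none uses the number of videos.

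**The case for a change.** The strongest case for acting is that payment is conditional on viewing, and viewing is the numerator of a primary outcome. If staff took two videos as enough, the incentive would stop at two while the percentage counted a third. A reader of the results might then be unable to separate low engagement from a schedule that went beyond what participants were asked about at entry. Payment terms should also be applied uniformly, and the literal word *both* together with the entry criterion gives the any-two reading some support.

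Part of this stands. The payment sentence does not fit a three-video week, and the documents reviewed do not settle it. The consent script and key information sheet were not available, so they cannot be counted on either way.

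The rest is weaker. Unequal payment for the same viewing would need staff to apply different readings to different participants, and one operational decision prevents that. The interpretive worry fades because the feasibility percentage cannot be computed without the number of videos sent. A reader given that number can see how far the schedule went beyond two a week. The larger figures (66.7%, $0 paid, a $60 gap) need three videos in all 12 weeks and a participant who watches exactly two in each of them.

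**Conclusion.** The inconsistency in wording is real, but it does not call for a change to the plan. The payment rule in a three-video week is ambiguous rather than undefined, and the more natural reading is that all videos sent that week must be viewed. The alternative reading is worth $5 for each three-video week in which a participant watches exactly two, at most $60 per person, with the number of such weeks unknown. The 80% split could be affected for such a participant only with seven or more three-video weeks, and then only as to which focus group the invitation is for. The primary percentage keeps its definition, and no estimate, test or conclusion changes under either reading.

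This rests on two assumptions: that the study team applies one reading of the payment rule to everyone in the SMS arm, and that the number of videos sent is reported with the feasibility percentage. The weekly number in sections 3.3 and 4.3 remains for the investigators to reconcile as a clerical matter; this review takes no view on which number is right.

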### Primary & Exploratory Outcomes

**Primary outcome: Feasibility:** Feasibility will be examined by calculating the percent of videos sent that are watched. We will also assess the feasibility by determining whether we are able to meet our recruitment goal of 30 Chinese American families and reach 80% retention rate.

**Acceptability:** Acceptability will be assessed using a satisfaction questionnaire adapted from a prior SMS intervention study.

**Secondary outcomes:** Consistent with our conceptual model (Fig. 1), we will also measure HbA1c, self-efficacy, and diabetes self-management behaviors at each time points (baseline, 3-, and 6-months). All of these scales have been used and validated in the Chinese population.

1. **HbA1c:** As part of the usual care, patients with T2D receive a HbA1c blood test at their doctors' office every 3-6 months. To minimize participants' burden, we will not conduct additional blood tests for this study. Instead, we will abstract the HbA1c testing results from the medical record at the participant's health care facility. Once we obtain the consent from participants, we will contact their doctors' offices for HbA1c results.

2. **Self-efficacy:** We will use the well-validated Stanford Diabetes Self-Efficacy Scale to measure participants' confidence to manage T2D. This instrument contains 8 items and asks participants to rate their confidence level in performing specific self-management behaviors, using 10-point Likert scale ranging from 1 (not at all confident) to 10 (totally confident).
3. **Diabetes Self-Management Behaviors:** We will administer the adapted Summary of Diabetes Self-Care Activities (SDSCA) measure to assess participants' adherence to diabetes self-management behaviors. This scale consists of 13 items and asks participants to describe their diabetes self-care activities over the past 7 days.
4. **Dietary Intake:** Informed by a previous study in Chinese Americans, we will use the adapted Mediterranean Dietary Screener to estimate dietary intake behaviors in our participants at baseline, 3- and 6-months.
5. **Physical Activity:** We will use the International Physical Activity Questionnaire (IPAQ) short version to assess the frequency and duration of various physical activities undertaken by adults over the past 7 days. This scale will provide an estimate of the number of minutes per week participants engage in each category of physical activity (e.g., vigorous, moderate, and mild intensity).

**Covariates: Sociodemographic, health characteristics, and acculturation.** We will use a sociodemographic questionnaire to collect basic information about the participant such as age, gender, education, income, duration of residence in the US, health insurance, the diabetes medication regimen, duration of T2D, and medical history. Informed by prior literature, we will also include surveys to measure Health Beliefs, Diabetes Knowledge, Diabetes Distress, Social Support, Mental Health, the Impact of COVID-19, and memory test, which also play essential roles in diabetes management.

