## **7. DATA ANALYSIS AND DATA MONITORING**

### **7.1 Data Analysis**

**Data analysis for Aim 1. Feasibility and acceptability:** Feasibility will be examined by calculating the percent of videos sent that are watched. We will also report the actual enrollment and retention rate. Acceptability will be examined by calculating percent of participants who report satisfaction with our intervention using a questionnaire adapted from a prior SMS intervention study.

**Data analysis for Aim 2.** We will employ the “intent to treat” (ITT) approach in analyses. We will perform a detailed descriptive analysis of all the data collected in the study. These preliminary descriptive statistics will be used to 1) check accuracy and completeness of inputted data, 2) describe univariate distribution of each variable at baseline, and 3) examine the associations between variables. We will also explore features of the data (e.g., amount and pattern of missing data, outliers, excess zeros, departures from distributional assumptions) to determine whether special techniques are needed.

**Aim 2: Proof of concept regarding the potential efficacy of the intervention for glycemic control.** We will test whether the 2 groups are comparable on baseline sociodemographic, health characteristics, and levels of acculturation. If significant differences are found, we will include the variables as covariates in the models. Between group and group by time interaction effects will be examined graphically and via linear mixed modeling for HbA1c. Calculated effect sizes will be used for sample size estimation needed for a two-sided alpha of 0.05 and power of 0.80 for the larger scale R01 study.

**Exploratory Aim: Explore the mediators of the SMS intervention.** Although underpowered, we will perform exploratory analyses of candidate mediators to evaluate the merit of further testing in a larger, adequately powered study. We will perform mediation analyses to determine whether self-efficacy and adherence to diabetes self-management explain significant variance in improvements in HbA1c.

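### Does the 80% retention target need a stated unit, visit and definition before it can serve as a feasibility outcome?

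*Combined protocol and SAP*

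**What the plan says.** The outcomes part of section 4.3 lists three feasibility measures: the percentage of sent videos that are watched, recruitment, and retention. The last two share one clause, "whether we are able to meet our recruitment goal of 30 Chinese American families and reach 80% retention rate". Section 7.1 adds only "We will also report the actual enrollment and retention rate".

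Other parts of the document bear on the unit and the timing:

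- **Pairs.** Section 3.1 sizes each arm as 15 pairs. Section 4.3 states "The patient and family/friend pair will be randomized via a computer-generated randomization scheme with equal allocation".
- **Individuals.** Section 3.3 counts 60 participants, "including 30 T2D Chinese patients and 30 corresponding family members". Payment is individual ("Both patient and family/friend participants will be paid"), and so is satisfaction ("Acceptability will be examined by calculating percent of participants who report satisfaction with our intervention").
- **Visits.** "The study will include 3 telephone-based measurement visits, baseline, 3, and 6 months". Section 3.1 gives the trial a duration of 6 months.
- **Data collection.** The procedures in section 4.3 place data collection at the telephone visit. HbA1c is abstracted from the medical record.

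**The concern.** Reaching 80% retention is phrased as something that is achieved or not, and it sits inside the primary outcome. A target of that kind should have a numerator, a denominator and a time point. Here all three are implicit. The intervention is delivered to dyads, so losing one member of a pair is a real loss. Yet counting individuals gives credit for the member who stays. There are also two follow-up visits, and retention at 3 months cannot be lower than at 6 months if nobody returns after dropping out. A patient who misses the call may still have an HbA1c value on record.

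At stake is whether a report could state that the target was reached under a reading chosen after the data were seen. This pilot is meant to inform a larger efficacy trial, so a flattering retention statement could carry forward.

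**Working it through.** **Base.** From section 3.1, 2 arms × 15 pairs = 30 pairs; × 2 members = 60 participants, which agrees with section 3.3. The documents give no derivation for the 80% itself. Applied to each possible unit, it means 0.80 × 60 = 48 individuals, 0.80 × 30 = 24 pairs, or 24 patients.

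**Range of complete pairs at 48/60.** Twelve individuals are lost. If *b* pairs lose both members, 12 − 2*b* pairs lose one. Complete pairs = 30 − *b* − (12 − 2*b*) = 18 + *b*, with *b* from 0 to 6. The range is therefore 18 to 24 pairs (60% to 80%).

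**Expected complete pairs at 80% individual retention.** If members drop out independently: 30 × 0.80² = 19.2. If they always drop out together: 30 × 0.80 = 24. The figure of 18 is the extreme case.

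**Chance that the unit changes the answer.** Let individual retention be *p* and within-pair correlation *r* (both assumed). Then P(both stay) = *p*² + *rp*(1 − *p*) and P(exactly one stays) = 2*p*(1 − *p*)(1 − *r*). An exact trinomial sum over 30 pairs gives:

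| *p* | *r* | P(≥48/60 individuals) | P(≥24/30 pairs) | P(first met, second missed) |
|---|---|---|---|---|
| 0.80 | 0 | 0.576 | 0.047 | 0.530 |
| 0.80 | 0.5 | 0.569 | 0.224 | 0.345 |
| 0.80 | 1 | 0.607 | 0.607 | 0 |
| 0.85 | 0 | 0.894 | 0.233 | 0.661 |
| 0.85 | 0.5 | 0.848 | 0.533 | 0.316 |
| 0.85 | 1 | 0.847 | 0.847 | 0 |
| 0.90 | 0 | 0.994 | 0.660 | 0.334 |
| 0.90 | 0.5 | 0.980 | 0.866 | 0.114 |
| 0.90 | 1 | 0.974 | 0.974 | 0 |

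The reverse (pairs met, individuals missed) cannot happen, because 24 complete pairs contain at least 48 individuals. That ordering does not extend to a patients-only unit. For example, 24 patients and 20 family members meet 24/30 patients, but make only 44/60 individuals.

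**Chance that the visit changes the answer.** Assume 30 pairs, no return after dropout and equal proportional loss per 3-month interval, so 3-month retention is the square root of 6-month retention. Because the 6-month target cannot be met without the 3-month one, the chance of meeting 24/30 at 3 months and missing it at 6 is the difference of the two binomial tails:

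| 6-month retention | P(met at 3 months) | P(met at 6 months) | Difference |
|---|---|---|---|
| 0.70 | 0.792 | 0.160 | 0.632 |
| 0.75 | 0.903 | 0.348 | 0.555 |
| 0.80 | 0.966 | 0.607 | 0.359 |
| 0.85 | 0.993 | 0.847 | 0.145 |
| 0.90 | 0.9993 | 0.974 | 0.025 |
| 0.95 | >0.9999 | 0.9994 | 0.0006 |

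The ambiguity bites when true retention lies near or below the target and fades quickly above it.

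**What the text supports as the default.** *Unit:* families are named in the same clause as the target, arms are sized in pairs, and the pair is randomized. The individual-level statements concern payment, viewing and satisfaction, which are naturally individual. *Visit:* the trial lasts 6 months and its last measurement is at 6 months, so retention ordinarily means the end of the study. *Retained:* data are collected at the telephone visit, which makes a completed call the ordinary criterion. The abstracted HbA1c is a data source, and nothing in the text treats it as evidence of retention.

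**The case for a change.** The strongest case for a change is that these are defaults and not definitions. Grammatically, the reference to families belongs to the recruitment goal. Even if it carries over, it does not say whether a family with one remaining member is retained. The 3-month visit is also a defensible choice, since the intervention ends at 12 weeks and the control group's completion payment is tied to that assessment. A stated definition would cost a sentence or two, with no new data.

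Most of this stands as description. The text is silent, and near 80% retention the choice can decide whether the target was met. What does not follow is that the plan must change. A request that leaves unit and visit to the sponsor would only write down a convention; it would alter no estimate, sample size or decision. Nor is a reader unable to check the result: that would be so only if the report left out the numerator, denominator and visit, and section 7.1 already promises the actual rate. With 30 pairs, the counts can be shown for both visits and all three units in a few lines.

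**Conclusion.** The observation is accurate, but it is a gap in detail that an analyst fills sensibly, and no change is needed. The default reading is complete pairs with a finished telephone assessment at 6 months, so 24 of 30 pairs. Other readings can give a different yes or no. At 85% individual retention and correlation 0.5, the individual and pair counts disagree with probability about 0.32 (0.66 if members drop out independently, 0 if they always leave together). At 80% six-month pair retention the two visits disagree with probability about 0.36, falling to 0.025 at 90%. All these rates and correlations are assumed.

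The consequence is limited to one descriptive statement. The 80% is not a progression rule and enters no comparison between arms. Viewing and satisfaction are measured separately, and the retention achieved is reported whether or not the target is met. The conclusion assumes that the report will give counts with their unit and visit, as is normal practice for a trial of this size.
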